Project Title: The Role of Different Prefrontal Areas in Visual Metacognition

NCT Number: NCT04263766

Date: 06/12/2023

Study Protocol

Metacognition refers to the ability to self-assess the quality of one's own decisions, and it is crucial for effective decision-making. A lot of prior research has focused on revealing the neural correlates underlying human confidence judgments, and many studies have pointed to a central role for the prefrontal cortex and specifically the dorsolateral prefrontal cortex (DLPFC).

However, although these studies made progress in discovering where confidence is computed in the brain, much less is known about the timing of confidence computation. A recent paper by Shekhar and Rahnev (2018) examined this question by delivering a train of three pulses of transcranial magnetic stimulation (TMS) to DLPFC at 250, 350, and 450 ms after stimulus onset in a perceptual decision-making task. From this study, they found that the TMS train of pulses decreased confidence compared to a control region (the primary somatosensory cortex) but could not determine exactly when confidence computation occurred.

To address more precisely the issue of when confidence computations occur, we here developed a protocol where we used single pulse TMS at four different times. Specifically, we delivered single pulses of TMS at 200, 300, 400, and 500 ms after stimulus onset and compared the results to TMS delivered simultaneously with stimulus onset (0 ms condition). The task for participants was to judge the orientation of a briefly presented visual stimulus and to report confidence ratings on the decisions. We delivered online TMS to DLPFC in the experimental group, and to vertex in the control group.

The main experiment comprised four sets, each consisting of five blocks with 40 trials in each block, resulting in a total of 800 trials. The possible delays for transcranial magnetic stimulation (TMS) - 0, 200, 300, 400, and 500 ms after the stimulus onset - were presented in a pseudorandom order. Within each group of five trials, each delay appeared once. The design and procedure were the same for both the DLPFC and vertex groups, except for the specific target site.

Before starting the experiment, participants underwent a behavioral training session without TMS. The training began with a high contrast value (80%) for Gabor patches and gradually decreased the contrast over subsequent blocks (the final block had a contrast value of 6%). Participants received feedback on their performance after each trial during the training. Following this, participants completed a staircasing procedure known as 3-down-1-up without feedback. This adaptive procedure estimated the appropriate contrast value for each individual participant. On average, this procedure yielded a mean contrast value of 6.64% (standard deviation = 0.96%). The contrast value obtained for each participant during this procedure was used for the rest of the experiment. At the end of the training, participants performed one practice TMS block with the same contrast level and TMS delivery as in the rest of the experiment. The practice block aimed to familiarize participants with receiving TMS while performing the task and was not included in further analyses.

During each trial of the task, participants initially fixated on a small white dot (0.05° in size) at the center of the screen for 500 ms. This was followed by the presentation of a Gabor patch (3° in diameter) that appeared either tilted to the right (45° clockwise) or left (135°

counterclockwise) relative to the vertical orientation, lasting for 100 ms. The Gabor patch was superimposed on a noisy background. Participants indicated the tilt orientation of the Gabor patch while simultaneously rating their confidence on a 4-point scale (1 denoting the lowest confidence and 4 denoting the highest confidence) by pressing a single key. The four fingers of the left hand corresponded to the four confidence ratings for the left tilt response, while the four fingers of the right hand corresponded to the four confidence ratings for the right tilt response. For each hand, the index finger represented a confidence rating of 1, while the pinky finger represented a confidence rating of 4. The stimulus orientation (left/right) was randomly determined on each trial.

Two sites were selected as TMS targets: the right dorsolateral prefrontal cortex (DLPFC) and the vertex. The right DLPFC was localized based on previous studies, using the F4 electrode position in the 10-20 system used for EEG electrode placement. Consistent with other studies targeting DLPFC with TMS during perceptual decision-making tasks, the right hemisphere was chosen as it is dominant for visual processing. To determine the precise stimulation location specific to each participant, we employed the Beam F3 Location System developed by Beam and Borckardt (2009). This method allowed us to accurately identify the F4 region using skull measurements. The vertex location was determined as the midpoint between the nasion and inion.

Statistical Analysis Plan

We conducted an analysis of confidence and metacognitive ability for each delay condition. Metacognitive ability was measured using the Mratio metric, which was developed by Maniscalco and Lau (2012). Mratio is based on signal detection theory and involves the observer's decision and confidence responses. It is calculated as the ratio of two measures: the observer's metacognitive sensitivity ($\text{meta-}d'$), which reflects their ability to distinguish between correct and incorrect responses, and the observer's stimulus sensitivity (d'), which reflects their ability to differentiate between the two stimulus classes. The $\text{meta-}d'$ to d' ratio accounts for the influence of stimulus sensitivity on metacognitive performance and captures the efficiency of the observer's metacognitive processes.

To investigate the impact of TMS on confidence and metacognitive ability (Mratio), we calculated the difference between the confidence and Mratio scores for each delay condition compared to the 0-ms condition. Subsequently, we employed one-way and two-way repeated-measures ANOVAs to compare the obtained difference scores between the two TMS stimulation sites (DLPFC and vertex) and the four TMS delay conditions (200, 300, 400, and 500 ms). Independent sample t-tests were used for direct comparisons between the two TMS stimulation sites within each delay condition, while paired t-tests were used for direct comparisons between different delay conditions within a single stimulation site.

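### Do the printed Gabor angles leave the tilt task without a signal, and Mratio without a denominator?

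*Combined protocol and SAP*

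**What the plan says.** The only physical definition of the two stimuli is in the Study Protocol, in the paragraph that describes a single trial. The patch was "tilted to the right (45° clockwise) or left (135" degrees "counterclockwise) relative to the vertical orientation, lasting for 100 ms". Both angles have a stated direction and both are referred to vertical. The sentence runs across a break in the extracted text, but its parenthesis closes properly and no words appear to be lost.

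The same paragraph continues: "Participants indicated the tilt orientation of the Gabor patch", with the left hand used for left tilt and the right hand for right tilt. It ends: "The stimulus orientation (left/right) was randomly determined on each trial".

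The paragraph before it reports how contrast was set: "participants completed a staircasing procedure known as 3-down-1-up without feedback". It then gives the outcome: "this procedure yielded a mean contrast value of 6.64% (standard deviation = 0.96" per cent).

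The Statistical Analysis Plan takes d' as the measure "which reflects their ability to differentiate between the two stimulus classes". Of Mratio it says: "It is calculated as the ratio of two measures: the observer's metacognitive sensitivity" (meta-d') and d'.

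**The concern.** The left/right classification underlies accuracy, the staircase, d', meta-d' and Mratio, and Mratio is one of the two outcomes analysed. If the two angles are one orientation, a task built to the text offers nothing to discriminate by tilt. Expected accuracy would be 50%, true d' would be 0, and Mratio would be a ratio to noise around zero. A fault of that kind in the trial itself would make the metacognition results meaningless, so the sentence needs checking against the rest of the document.

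**Working it through.** **Step 1: the geometry.** Inputs are the two angles in the trial-procedure paragraph. Count clockwise from vertical as positive and reduce modulo 180, because a grating rotated by 180 degrees has the same orientation.

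| Reading | Right class | Left class | Separation |
|---|---|---|---|
| As printed (45 clockwise, 135 counterclockwise, from vertical) | 45 mod 180 = 45 | -135 mod 180 = 45 | 0 degrees |
| Left taken as 45 counterclockwise from vertical | 45 | -45 mod 180 = 135 | 90 degrees |
| Both angles clockwise from vertical | 45 | 135 | 90 degrees |
| Both angles counterclockwise from horizontal | 90 - 45 = 45 | (90 - 135) mod 180 = 135 | 90 degrees |

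The stated pair does not reproduce as two classes. A numerical check with constructed patches agrees. As printed, the two patches correlate at 1.0 in cosine phase and at -1.0 in sine phase (same orientation, contrast reversed). A patch 45 degrees clockwise and one 45 degrees counterclockwise correlate at about 0. The other three readings in the table all give a right tilt and a left tilt 90 degrees apart.

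**Step 2: what the literal reading would do.** With no orientation signal the hit rate H equals the false-alarm rate F, so d' = z(H) - z(F) = 0. That is a defined value. Only Mratio = meta-d'/d' loses its definition, because its true denominator is 0. With 800 trials over 5 delays there are 800/5 = 160 per delay. Assume 80 per class. The large-sample SD of estimated d' at H = F = 0.5 is then sqrt(2 × 0.25 / (80 × 0.3989²)) = sqrt(0.5/12.73) = 0.198. A simulation gave mean 0.001 and SD 0.196, with 47% of estimates negative.

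**Step 3: does the reported staircase fit that reading?** In a 3-down-1-up rule each cycle ends in three correct responses (a step down) or an error (a step up). With equal steps, which is an assumption because step sizes are not given, the rule settles where p³ = 0.5:

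- p = 0.5^(1/3) = 0.794, and for an unbiased observer d' = 2 × z(0.794) = 1.64.
- Under guessing, p³ = 0.5³ = 0.125, so the chance of a step up is 1 - 0.125 = 0.875. That is seven steps up for each step down, and contrast climbs.

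The reported result is a mean of 6.64% with SD 0.96%. Mean ± 2 SD is 6.64 ± 1.92, or 4.72% to 8.56%. Training started at 80% contrast and ended at 6%, so the staircase settled close to the lowest training level, and did so consistently across participants. Discriminable stimuli would give this result; guessing would not.

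**Step 4: the labels.** The staircase alone rules out identical images. It does not rule out a pair with one orientation and reversed contrast polarity, and the documents do not state the phase. The wording does that: the stimuli are called right and left tilts, participants judged tilt, each tilt had its own hand, and training gave feedback after each trial.

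**The case for a change.** The best case for acting is that this sentence alone defines the stimuli, that no reading rescues it as printed, and that correcting it would cost one sentence and a look at the stimulus script. A team rebuilding the task from the angles alone would produce two patches with the same tilt. All of that stands: at least one printed number, direction or reference axis is wrong, and the intended angle is an inference that only the stimulus code can confirm.

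The step from there to the trial's outcomes does not stand. The document is written in the past tense about a task already completed, so a replica built to the faulty angles is hypothetical. The wording around the angles names two opposite tilts throughout, and a replicator would find the mismatch on first viewing the patches. The phrase about two stimulus classes in the Statistical Analysis Plan contains no error.

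One caution applies to the reply as well. The staircase's starting contrast, step sizes and length are not reported, so its result is strong evidence of discriminable stimuli but not proof.

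**Conclusion.** The left-tilt angle as printed contradicts its own label: it is 0 degrees from the right-tilt angle, where 90 degrees was almost certainly meant. This is a clerical slip, probably a wrong direction of rotation or two angle conventions mixed. It affects exact replication of the stimulus and nothing else. No procedure, comparison between sites or delays, d' or Mratio value, or conclusion depends on how the angle is printed, so the plan needs no change.

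The conclusion rests on two assumptions: that the left and right labels describe what was shown, and that the staircase steps up and down were of comparable size. Nothing in the documents suggests otherwise.

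### Confidence is compared across sites and delays with no planned comparison of d', so a perceptual effect of the pulse could be read as an effect on confidence computation

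*Combined protocol and SAP*

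**What the plan says.** The Statistical Analysis Plan section names two outcomes: "We conducted an analysis of confidence and metacognitive ability for each delay condition". The scores tested are changes from the 0-ms condition: "we calculated the difference between the confidence and Mratio scores for each delay condition compared to the 0-ms condition". These scores go into the ANOVAs over two sites and four delays, and then into two sets of follow-up tests: "Independent sample t-tests were used for direct comparisons between the two TMS stimulation sites within each delay condition", and "paired t-tests were used for direct comparisons between different delay conditions within a single stimulation site".

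Stimulus sensitivity (d') appears only in the definition of Mratio, where the ratio is said to be one that "accounts for the influence of stimulus sensitivity on metacognitive performance". Nothing similar is said about raw confidence.

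The Study Protocol section describes how task difficulty was set. Before the experiment, "participants underwent a behavioral training session without TMS". "Following this, participants completed a staircasing procedure known as 3-down-1-up without feedback". Then: "The contrast value obtained for each participant during this procedure was used for the rest of the experiment". The stated aim is to find out when confidence is computed.

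**The concern.** Confidence normally follows the strength of the evidence. If a pulse changes how well the stimulus is perceived, ratings can move although nothing has happened to the process that turns evidence into confidence. The plan needs a way to notice this, and for the confidence outcome it has none.

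The design deals with part of the problem. Each delay occurs once in every five trials, so slow drift is balanced across delays. The vertex group removes pulse effects common to both sites. Neither removes a d' change that occurs only with DLPFC stimulation and only at one delay. The staircase cannot help, because contrast was fixed without TMS and not adjusted afterwards.

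Mratio does not settle the matter. It measures metacognitive efficiency, not the level of confidence. In a fixed-criterion model in which d' falls through loss of signal, meta-d'/d' stays at 1 while mean confidence drops. The plan could then report a confidence effect with Mratio unchanged and attribute it to the timing of confidence computation.

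The 0-ms reference needs separate care, because it is the only pulse that falls within the 100-ms stimulus. A site-specific d' change there would enter every difference score.

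**Working it through.** The plan states no d', accuracy, group size or effect size, so there is no figure of its own to reproduce. What follows is an illustration under stated assumptions.

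**Inputs from the documents.** Trials: 4 sets x 5 blocks x 40 = 800, so 800/5 = 160 per delay. Staircase: 3-down-1-up. Scale: 1 to 4.

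**Assumptions.** Equal up and down steps; an unbiased equal-variance signal-detection observer; fixed confidence cut-offs on |x|, in four sets: (0.5, 1.0, 1.6), (0.4, 0.9, 1.4), (0.6, 1.2, 1.8), (0.3, 0.7, 1.2); the size of the d' fall; group sizes of 15, 25 or 40; and the between-person SDs.

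**Baseline d'.** The staircase converges where p^3 = 0.5, so p = 0.794 and d' = 2 x z(0.794) = 1.64. A 0.2 fall takes accuracy from 79.4% to 76.4%.

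**Shift in mean confidence.** Mean confidence is 1 plus the sum over cut-offs c of P(|x| > c), with x normal, mean d'/2 and SD 1 at baseline. Signal loss lowers the mean. Noise gain keeps the mean and raises the SD to 1.64/(1.64 - fall), which is 1.14 for a 0.2 fall. The equal split shares the log of the d' ratio between the two. Ranges are over the four cut-off sets.

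| Fall in d' | Signal loss | Noise gain | Equal split |
|---|---|---|---|
| 0.1 | -0.036 to -0.039 | +0.030 to +0.042 | not tabulated |
| 0.2 | -0.070 to -0.077 | +0.064 to +0.089 | -0.002 to +0.007 |
| 0.3 | -0.103 to -0.113 | +0.103 to +0.143 | not tabulated |

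**Size against sampling error.** For one within-delay site comparison, SE = sqrt(2/n x (2 x SD^2/160 + b^2)). The trial SD of confidence is 1.08 to 1.13 (from the model), and b, the between-person SD of the true confidence change, runs from 0 to 0.2.

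| n per group | SE | 0.2 fall, one mechanism, in SEs |
|---|---|---|
| 15 | 0.044-0.086 | 0.7-2.0 |
| 25 | 0.034-0.067 | 1.0-2.6 |
| 40 | 0.027-0.053 | 1.2-3.3 |

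**A 0.2 fall at 0 ms only, in the DLPFC group** (25 per group, cut-offs 0.5/1.0/1.6, baseline d' SD 0.3). The spurious site main effect (DLPFC minus vertex) is about +0.075 with signal loss and -0.09 with noise gain. The same offset enters all four within-delay site t-tests. It is common to the four difference scores, so it cancels in the site x delay interaction and in paired tests between later delays. In simulation both reject at about the nominal 5%.

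**What a d' comparison could show.** The simulated SD of one participant's d' change is 0.32, 0.38 or 0.51 when the true change has a between-person SD of 0, 0.2 or 0.4. The 95% half-width is t x SD x sqrt(2/n).

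| n per group | SD of true change 0 | 0.2 | 0.4 |
|---|---|---|---|
| 15 | 0.24 | 0.28 | 0.38 |
| 25 | 0.18 | 0.22 | 0.29 |
| 40 | 0.14 | 0.17 | 0.23 |

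**Adjusting confidence for observed d' change** (25 per group, 0.2 fall, between-person SDs of 0, 0.2 and 0.4 in turn). With signal loss, adjustment removes roughly 32-38%, 50-54% and 70-79% of the spurious effect. With noise gain, it enlarges the effect by about 26-35%, then removes 1-11% and 45-51%.

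**The case against.** The best counter-argument accepts that no d' comparison is listed and disputes how much that matters.

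- **No evidence of a perceptual effect.** Nothing in the documents shows that the pulse changes d', and the four delays of interest all fall after the 100-ms stimulus has ended. This stands: the figures show possibility only. But d' can still be affected after stimulus offset, and the plan has no check for it.
- **The bias has no fixed sign.** Depending on mechanism it is negative, positive or near zero. Only signal loss mimics the fall in confidence that the Study Protocol reports from the earlier study. The largest value in standard errors comes from noise gain, no between-person variation and 40 per group. This also stands, and it is why d' has to be looked at and cannot simply be corrected for.
- **A d' comparison would not settle the cause.** At 25 per group the half-width is 0.18 to 0.29, about the size of the shift illustrated. With no between-person variation, an estimate of zero would just exclude a change of 0.2; at an SD of 0.2 or more it would not. The comparison is therefore a check on interpretation, not proof. It still limits what the confidence result can be taken to show.
- **The 0-ms issue is secondary.** It cancels in the contrasts that compare later delays with each other. That is correct, but it remains in the site main effect and in the within-delay site tests, both of which are planned.

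**Conclusion.** The concern holds. Nothing in the plan compares d' or accuracy between sites or delays, and raw confidence is neither adjusted for nor matched on performance. A site difference in confidence at one delay therefore cannot be told from a perceptual effect of the pulse at that delay by any planned analysis.

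Under the assumed model, a 0.2 fall in d' by one mechanism alone moves mean confidence by roughly 0.06 to 0.09 points in either direction, or about 1.0 to 2.6 standard errors of a within-delay site comparison at an assumed 25 per group. A mixture of mechanisms can bring the shift close to zero. The model, cut-offs, d' falls, group sizes and between-person SDs are not in the documents, so none of this measures how likely the problem is. The gap itself does not depend on them.

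The point concerns the confidence outcome. Mratio has its own correction for d'. The planned tests remain computable; what is weakened is the inference about timing drawn from confidence. The plan should be changed, with moderate confidence in how much the change matters.

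**What to change.** Add d' as a supporting outcome in the Statistical Analysis Plan.

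1. Run the same site x delay ANOVA and within-delay site t-tests on d', as change from 0 ms.
2. Report, with 95% confidence intervals, the site difference in d' change at each of the four delays and the site difference in d' at 0 ms.
3. Interpret confidence effects beside these intervals. State that a non-significant d' test does not by itself exclude a perceptual explanation, and that a d' change makes one possible without establishing it.
4. Note that a similar site difference in d' change at all four delays may come from the 0-ms reference. Treat the 0-ms site difference as descriptive: every main-experiment trial carries a pulse, so it mixes any pulse effect with ordinary differences between the groups.
5. Use a d'-adjusted analysis of confidence, if added, as a sensitivity analysis only. Observed d' change is noisy and measured after stimulation, so adjustment is incomplete by an unknown amount and can enlarge the effect.

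The cost is a few sentences and a small extra analysis of data already collected. The price is a more cautious conclusion if d' also shifts or is imprecisely estimated.

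### The site comparisons that would name a delay are unadjusted over four delays and not tied to the ANOVAs, so the false-positive risk per outcome could lie anywhere from about 1% to 18%

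*Combined protocol and SAP*

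**What the plan says.** The Study Protocol section sets the aim. An earlier study with a three-pulse train "could not determine exactly when confidence computation occurred", and the present design uses single pulses "To address more precisely the issue of when confidence computations occur".

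The Statistical Analysis Plan section covers two outcomes: "We conducted an analysis of confidence and metacognitive ability for each delay condition". For each it "calculated the difference between the confidence and Mratio scores for each delay condition compared to the 0-ms condition", which leaves four difference scores per participant (200, 300, 400 and 500 ms). It continues: "Subsequently, we employed one-way and two-way repeated-measures ANOVAs to compare the obtained difference scores", across the two sites and four delays. Two sets of t-tests follow. Between sites, "Independent sample t-tests were used for direct comparisons between the two TMS stimulation sites within each delay condition"; within a site, "paired t-tests were used for direct comparisons between different delay conditions within a single stimulation site".

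Neither section gives a significance level or a multiplicity rule, or says that the t-tests are run only after a significant ANOVA term. The sequencing word at the start of the ANOVA sentence places the ANOVAs after the difference scores; it does not make the t-tests conditional on them.

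**The concern.** The site-by-delay interaction is one omnibus test. It can show that the site effect varies with delay, but it cannot say at which delay the sites differ. The between-site t-tests do that, and there are 4 delays × 2 outcomes = 8 of them. A chance difference at one delay could therefore be reported as a time at which DLPFC stimulation affects confidence.

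How likely that is depends on whether the t-tests are gated by an ANOVA, and on which term. The plan leaves both open, so a reader cannot attach an error rate to a claimed delay.

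**Working it through.** **Inputs from the documents.** Four delays, two outcomes, two separate groups, a shared 0-ms reference, independent t-tests between sites, and a two-way ANOVA with site and delay. The plan states no error rate or power, so there is no figure of its own to reproduce.

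**Assumptions, because the documents give no values.** Two-sided 0.05 per test; normal scores with equal variances; equal groups. The correlation between difference scores is taken from 0.2 to 0.8, with 0.5 as the base case. If the five raw conditions have common variance s² and common correlation r, then

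- covariance of (X_i − X_0) and (X_j − X_0) = s²(r − r − r + 1) = s²(1 − r)
- variance of each difference = 2s²(1 − r)
- correlation = s²(1 − r) / [2s²(1 − r)] = 0.5, whatever r is.

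**Step 1: upper reference.** Four independent tests would give 1 − 0.95⁴ = 0.185. Positive correlation lowers this.

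**Step 2: no TMS effect, one outcome.** Simulation, 100,000 studies per setting. Each study has four pooled t-tests and a 2 × 4 mixed ANOVA, with site tested on F(1, 2n − 2) and interaction on F(3, 3(2n − 2)). An error is any between-site p below 0.05 that passes the gate.

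| How the t-tests are used | Correlation 0.5, 10-50 per group | Correlation 0.2 to 0.8, 20 per group |
|---|---|---|
| Stand alone | 15.5-15.8% | 18.0% to 11.5% |
| Gated on site or interaction | 6.8-7.3% | 7.6% to 6.0% |
| Gated on site only | 4.5-4.8% | 3.9% to 5.0% |
| Gated on interaction only | 2.5-2.7% | 3.9% to 1.3% |
| Bonferroni, 0.05/4 = 0.0125 | 4.2-4.5% | 4.8% to 3.2% |

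With no true effect, Holm makes an error exactly when Bonferroni does, so the last row applies to Holm too. Group size hardly matters here; the correlation does.

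**Step 3: both outcomes, stand-alone t-tests.** Over all eight tests at correlation 0.5, the rate is about 29% if the outcomes are independent and 23-24% if they correlate 0.8.

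**Step 4: a real effect at some delays.** The error is now a false site difference at an unaffected delay. Assumed 25 per group, correlation 0.5, true effect 0.5 to 0.8 SD of the difference score.

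| Truly affected delays | Stand alone | Interaction gate | Holm |
|---|---|---|---|
| One | 12-13% | 7-11% | 4% |
| Two | 9% | 6-8% | 3-4% |

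With one affected delay, the interaction gate opens in 40% of studies at 0.5 SD and 83% at 0.8 SD. Once open, it gives the unaffected delays no further protection. A gate on site or interaction lets through 10-12%. Leakage through a site-only gate is not part of this table.

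**Step 5: power at an assumed 25 per group.** The noncentrality is δ√(n/2): 0.5 × √12.5 = 1.77 and 0.8 × √12.5 = 2.83, on 48 degrees of freedom. The critical |t| is 2.01 unadjusted and 2.60 at Holm's first step.

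| True effect at one delay | Unadjusted | Interaction gate | Holm over four | Holm over eight |
|---|---|---|---|---|
| 0.5 SD | 41% | 25% | 22% | 15% |
| 0.8 SD | 79% | 71% | 59% | 49% |

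**The case against.** The strongest reply is that the t-tests are ordinary follow-up to the ANOVA. The plan lists the ANOVAs first, and this is the natural reading. A reader might infer from the first row of Step 2 that the study carries a 16% or 18% error rate. The documents do not support that: it is the rate for stand-alone tests, and they do not say the tests stand alone. With an interaction gate and no effect anywhere, the risk is below 5%. This part of the reply stands. It does not close the matter, because the plan names neither a gate nor a term, and Step 4 shows that an interaction gate leaks once something real is present.

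The leakage figures with one affected delay are the least favourable of the cases examined. The earlier pulse train spanned 250 to 450 ms, so effects at neighbouring delays are plausible. With two affected delays, the gap between gate and Holm narrows to 6-8% against 3-4%. That also stands.

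The four ways of using the t-tests in Step 2 are not exhaustive. The plan also mentions one-way ANOVAs, and a gate on those was not examined.

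Holm has a real price, and a mechanistic study may reasonably value sensitivity. This argues for showing adjusted and unadjusted results together, not for omitting the adjustment.

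The aim in the Study Protocol points to confidence as the leading outcome, though the project title concerns metacognition and the Statistical Analysis Plan describes Mratio at greater length. The text is in the past tense and reports that "this procedure yielded a mean contrast value of 6.64" per cent. A reader might infer that any lead outcome would be chosen after seeing results. The documents show only that a calibration value was known; they do not say when outcome data were seen.

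**Conclusion.** The concern holds in a limited form. Eight between-site tests carry the timing question, with no adjustment and no stated link to the ANOVAs. Under the assumptions listed, the per-outcome risk with no effect is about 18-12%, 8-6%, 4-5% or 4-1%, depending on how the tests are used. With one or two truly affected delays, an interaction gate leaves 6-11% and Holm 3-4%.

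The rates with no effect are stable across group sizes but move with the correlation. The leakage and power figures also depend on an assumed 25 per group and on which delays are affected.

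A reader might go further and conclude that a reported delay effect is false, or that an ANOVA gate is worthless. Neither follows. The point is about an error rate the plan leaves open; it says nothing against any particular result, and an interaction gate is adequate when no delay has an effect. The 24 within-site paired tests (6 pairs × 2 sites × 2 outcomes) are outside these figures.

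**What to change.** 1. For confidence, the outcome in the timing aim, report Holm or max-T adjusted p-values for the four site contrasts, beside unadjusted p-values and confidence intervals for all four delays.
2. Do the same for Mratio as a separate family.
3. State that error is controlled within each family only. With no effect, at correlation 0.5, the rate over both Holm families together is 8-9% if the outcomes are independent and 7% if they correlate 0.8.
4. Base any claim about a specific delay on the adjusted values.
5. If confidence was not chosen as lead before outcome data were seen, say so and also report Holm over all eight contrasts. This holds the overall rate at or below about 4-5% and needs no choice of lead.

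The cost is a few lines of text and code, with no new data. The downside is the loss of power per delay in Step 5: 41% to 22% at 0.5 SD and 79% to 59% at 0.8 SD, and further with eight contrasts. Showing the unadjusted values and intervals keeps the information visible. If outcome data were already seen, wording cannot make a lead outcome named now prospective.
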